### 199 **Adherence assessments**

200 Multiple methods will be used to assess treatment adherence including pill  
201 counting; reasons for non-compliance, and use of the capsules. Participants will  
202 return each week to receive new capsules. All treatment data will be recorded on  
203 the appropriate case report form.

204 **Dietary analysis**

205 All participants will be subjected to a nutritional survey to define the daily calories  
206 required to establish a custom diet. Dietary intake will be monitored through  
207 retrospective methods including the 24 h recall (which investigates intake over a  
208 specific day), and the food frequency questionnaire (a summary of usual intake of  
209 different categories of foods). These accurate and validated techniques allow  
210 quantifying the types and quantities of foods and beverages consumed during the  
211 period of interest in the past. Dietary intake evaluations will be performed at each  
212 MIT of the study in order to record the possible variability in food consumption  
213 patterns.

214 **Physical exercise protocol**

215 General health assessment and physical activity questionnaires (PAR-Q and YOU)  
216 will be conducted; this will be done to ensure that there are no physical  
217 impediments to exercise. GEx participants are going to exercise five days a week  
218 with the following protocol: between 5 and 10 min of warm-up exercise, between  
219 20-30 min muscular endurance exercise and 20-30 minutes of aerobic exercise  
220 (cardiovascular exercise): walking, jogging, running and/or cycling. Three days a  
221 week aerobic intensities will be between 60% and 80% and two days between 70%  
222 and 90% of the maximum HR reserve, and five final minutes of stretching.

223 **Sample collection and biochemical analysis**

224 Blood samples (8 mL) will be collected before and after each MIT from the  
225 antecubital vein into ethylenediaminetetraacetic acid (EDTA) tubes after 10-12 h of

226 fasting, plasma from blood samples will be obtained by refrigerated centrifugation  
227 (4°C) at 5 000 g for 10 minutes. Plasma glucose TC, HDL-c, LDL-c, and TAG  
228 concentrations will be analyzed by using standard enzymatic procedures (Jas  
229 Diagnostics, Inc. Mexico) with a spectrophotometer (Genesys 10 UV; Thermo  
230 Electron Corporation, USA). Plasma will be used to measure MDA and GSH  
231 content and activity of GPx and GR according to Jimenez-Osorio *et al.*, total  
232 antioxidant status (TAS) by 2,2-diphenyl-1-picrylhydrazyl (DPPH) technique as  
233 previously described by Koren *et al.*, oxygen radical absorbance capacity  
234 (ORAC) following Prior *et al.* methodology. The erythrocytes will be washed with  
235 cold 0.9% saline solution twice and are going to be used for SOD and catalase  
236 activity assays as previously described by Jimenez-Osorio *et al.*, and plasma  
237 PON1 content will be measured by following Perez-Herrera *et al.* methods.

### 238 **Statistical analysis**

239 To evaluate data distribution, normality and homoscedasticity tests on each of  
240 response variables analyzed will be conducted. In order to analyze differences  
241 between variables before and after the study and between the groups, an ANOVA  
242 test will be performed. To analyze possible associations between variables, a  
243 bivariate correlation analysis will be used. To analyze independence between  
244 variables, a multiple regression analysis will be performed. The software to use is  
245 GraphPad Prism 6.

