#### 91 **Outcome measures**

92 The primary outcome measure will be changes in the plasma lipid profile after a  
93 six-week of treatment (plasma TAG, TC, HDL-c, and LDL-c by using standardized  
94 enzymatic methods).

95 The secondary outcome measure will be changes in general fitness (maximal  
96 oxygen uptake ( $VO_2$  max), heart rate (HR), in onset blood lactate accumulation,  
97 and body fat mass); as well as changes in redox status (malondialdehyde (MDA),  
98 protein carbonyls, paraoxonase (PON1), superoxide dismutase (SOD), catalase  
99 glutathione (GSH), glutathione reductase (GR), and glutathione peroxidase (GPx).

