### 136 **Study design**

137 The study consists of *S. maxima* treatment during 14 weeks in a randomized,  
138 double-blind, placebo-controlled, and counterbalanced crossover design, aimed to  
139 eliminate inter-individual bias as well as boosting the reliability of final results;  
140 moreover, this design is commonly used in clinical trials in order to have better  
141 results and conclusions . Eligible participants (n= 80) will be divided into two  
142 groups, one with systematic practice of physical exercise (GEx) and other one  
143 without it (GNEx). The participants of each group will be randomized in equal  
144 proportions between *S. maxima* and placebo treatment, receiving either 4.5 g daily,  
145 in a non-transparent capsule during 12 weeks (6 weeks for the first treatment - 2  
146 weeks of washout period - 6 weeks for the second treatment) (Figure 1). Before  
147 any reported allergic reaction occurs, the treatment will be discontinued.

148 To maintain the overall quality and legitimacy of the clinical trial, code interruptions  
149 should occur only in exceptional circumstances when knowledge of the actual  
150 treatment is essential for further management of the participant. Investigators are  
151 encouraged to discuss with a Medical Advisor if they believe that unblinding is  
152 necessary. Unblinding should not necessarily be a reason for study  
153 discontinuation.

154 A student outside the research team will feed data into the computer in separate  
155 datasheets, so that the researchers can analyze the data without having access to  
156 information about the allocation treatments, storing all the participants' files in  
157 numerical order in a safe and accessible place. The participants' files will be stored  
158 for a period of five years after the end of the study.

159 The sample size was determined by using the statistical program G\*Power ,  
160 selecting a sample of 73 subjects with  $\alpha = 0.05$  and  $p = 0.85$ . This sample will be  
161 fixed to 80 subjects in order to anticipate the possible desertions from the study.

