## 162 **Maximum intensity tests**

163 Each subject will participate in four stress tests performed at maximum intensity  
164 (MIT) during the study; during MIT record, consumed O2 and produced CO2 will be  
165 taken by a gas analyzer (Cortex MetaLyzer® 3B, Germany), HR with a Polar H7  
166 sensor (Polar Electro, Lake Success, NY), and lactate in capillary blood samples  
167 will be assayed in a YSI 1500 Sport Lactate Analyzer (YSI Life sciences, OH,  
168 USA). The MIT protocol consists of using a cycle ergometer (Monark ergomedic  
169 828 E; Monark exercise AB, 105 Vansbro, Sweden) initiating with a workload of 50-  
170 75 W with increments of 15-30 W every 3 min for until 15 min or when the subject  
171 could no longer pedal more than 40 revolutions/min, finishing the test when  
172 reaching 90-100 % of the maximum HR reserve; MIT will not be valid for less than  
173 9 min (Figure 2). At the end of each increment load (3 min), capillary blood  
174 samples will be taken to determine lactate, and the physical perceived effort will be  
175 registered by using the Borg scale. Measurements of HR, glucose and blood  
176 pressure will serve to take care of the subject's health during each MIT.

177 Before the first MIT, subjects will decide to be in the GEx or GNEx, and then they  
178 will be divided randomly for the treatment, which consists in a daily dosage of 4.5 g  
179 of Spirulina or placebo in capsules which will be recommended the subjects to  
180 consume them before each meal every day during six weeks. The day after the  
181 first supplementation period, subjects will come back to perform the second MIT

182 with identical conditions to the first one. The third MIT will be performed after a  
183 washout period of two weeks to remove the effects of treatment and avoid any  
184 possible delayed effect of *S. maxima* in the organism. The last MIT will be  
185 performed after the second treatment with identical conditions to the previous three  
186 times. General fitness parameters will be measured the same day of all the MITs to  
187 have accurate results.

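### The plan specifies neither the within-person Spirulina-minus-placebo comparison at six weeks nor a Spirulina-by-exercise test, and its one ANOVA sentence, read literally, does not isolate Spirulina

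*Combined protocol and SAP*

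**What the plan says.** The Study design section sets out a "double-blind, placebo-controlled, and counterbalanced crossover design, aimed to" remove between-person variation: six weeks on one treatment, two weeks of washout, six weeks on the other. Under Maximum intensity tests (MITs) there are four test occasions: baseline, end of period 1, after washout and end of period 2.

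Under Outcome measures, "The primary outcome measure will be changes in the plasma lipid profile after a" six-week course of treatment, for four lipids. The Objectives section seeks both independent and synergistic effects of Spirulina and exercise.

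Exercise is not randomised: "Before the first MIT, subjects will decide to be in the GEx or GNEx, and then they" are allocated to Spirulina or placebo.

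The Statistical analysis section is one paragraph. It names distribution checks, a comparison of differences "between variables before and after the study and between the groups, an ANOVA" being the test, a bivariate correlation, and, to study independence between "variables, a multiple regression analysis will be performed. The software to use is" GraphPad Prism 6. It does not define the groups. It names no participant, period, sequence or treatment term, and no interaction.

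**The concern.** By the end of the study every completer has taken both treatments. A comparison of before with after the whole study is therefore not a comparison of Spirulina with placebo. The only groups the text names outright are the exercising (GEx) and non-exercising (GNEx) groups, which participants choose for themselves. The contrast that a crossover exists to provide, each person's Spirulina period against their own placebo period, is not written down.

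The primary conclusion is at stake. Under some plain readings a diet, training or time trend would be reported as a Spirulina effect, or a real effect would be missed. Such trends are plausible: Dietary analysis gives everyone a custom diet, and the Physical exercise protocol has GEx training five days a week. The synergy objective has no specified test.

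**Working it through.** **The plan's own figure.** The 73 in Study design cannot be reproduced, because no effect size, SD, correlation or test is given. A paired standardised effect of about 0.355 would yield 73 at two-sided 5% and 85% power, but that is back-solved. The step to 80 allows for 1 − 73/80 = 8.75% loss.

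**Inputs.** From the documents: visits at weeks 0, 6, 8 and 14 (MIT 1 to 4), 1:1 allocation, n = 73, alpha 0.05, and 0.85, read here as power. Assumed: two-sided tests, equal correlation ρ between visits, complete washout, sequences of 37 and 36.

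**Step 1: what each reading estimates.** Let τ be the Spirulina effect and g the 14-week trend. MIT 4 minus MIT 1 averages g when Spirulina comes first and g + τ when placebo comes first.

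- Pooled over participants: g + τ/2, so half the effect plus all of the trend.
- GEx minus GNEx: τ/2 cancels when sequences are balanced within each group, leaving only the difference in trends.
- Between sequences: (g + τ) − g = τ. This isolates Spirulina but uses only the second period's treatment contrast.
- Within person, on MIT 2 minus MIT 4, with h the trend between them: [(τ − h) − (−τ − h)]/2 = τ. Trend removed, both periods used.

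**Step 2: standard errors.** Let σ be the SD of a single value and s the SD of the difference between two visits in one person, s = σ√(2(1 − ρ)).

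- End-of-period crossover contrast: (s/2)√(1/37 + 1/36) = 0.117s.
- Six-week-change contrast: variance 4σ²(1 − ρ) = 2s² per person, so 0.117s × √2 = 0.166s.
- Whole-study change between sequences: s√(1/37 + 1/36) = 0.234s. This is 2.0 times the first and 1.41 times the second.
- Pooled whole-study change: s√(1 + τ²/(4s²))/√73, which is 0.119s at τ = 0.356s.

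**Step 3: power (noncentral t).**

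| Analysis | τ = 0.356s (85% on end values) | τ = 0.503s (85% on six-week change) |
|---|---|---|
| End-of-period crossover | 0.356/0.117 = 3.04: 85% | 99% |
| Six-week-change crossover | 56% | 0.503/0.166 = 3.04: 85% |
| Pooled whole-study change | 0.178/0.119 = 1.50: 31% | 54% |
| Whole-study change between sequences | 0.356/0.234 = 1.52: 32% | 56% |

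**Step 4: a trend with no Spirulina effect.** The pooled test has noncentrality (g/σ)√73/√(2(1 − ρ)). For an assumed g of 0.1σ this is 0.854 at ρ = 0.5 and 1.351 at ρ = 0.8, giving a significant result in 13% and 27% of trials. For 0.2σ the figures are 39% and 76%. The documents state no trend, so these show direction only.

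**Step 5: the interaction.** With equal exercise groups its SE is 2s/√73 = 0.234s. For an interaction as large as τ = 0.356s, power is 32%. At n = 80 the SE is 0.224s and power 35%.

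**Step 6: regression as a substitute.** For participants with both periods, regressing MIT 2 minus MIT 4 on sequence (+1/−1) and exercise group gives exactly the treatment estimate of the mixed model in the fix. If the product term is added with exercise coded 0/1, the sequence coefficient becomes the effect in the reference exercise group only. In one simulated data set split 55/18 it was 0.26 against 0.48 from the primary model.

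**The case against.** ANOVA is a generic term. A repeated-measures ANOVA with participant, period, treatment and exercise terms is still an ANOVA. Read beside the six-week outcome and the tests placed at both ends of each period, a per-period comparison is a plausible intention. That stands. A reader might infer that the stated ANOVA cannot fit a crossover; the documents do not support that, because a sound reading is permissible. What remains is that the text does not choose it, and the readings estimate different quantities.

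The listed multiple regression could carry an interaction, so the plan is not without a usable method for synergy. But its outcome and terms are not given.

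Blinded handling of the data also helps: treatments are held in separate "datasheets, so that the researchers can analyze the data without having access to" allocation. This limits choosing an analysis by its result. It does not say which contrast is primary.

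The groups may be defined in Figure 1, which was not available; its legend could mean four exercise-by-sequence groups. An allocation figure would still not supply an error term or a contrast.

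Finally, the power figures rest on assumed inputs. They illustrate the cost of the ambiguity. The omission is shown by the text alone.

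**Conclusion.** The concern holds as a failure of specification. The plan fixes neither the comparison that decides the primary outcome nor the test of synergy, and its one comparative sentence, followed literally, does not isolate Spirulina. This should be corrected before analysis.

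On size: about 31% power for the pooled reading and 32% for the between-sequence reading, against 85% for the end-of-period crossover contrast. These assume n = 73, equal correlations, complete washout and an effect calibrated to end-of-period values. With the effect calibrated to six-week change the two figures are about 54% and 56%.

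Two further inferences go too far. The between-sequence SE is not simply double: it is twice that of the end-of-period contrast but about 1.4 times that of the six-week-change contrast, which is closer to the stated outcome. Nor do these figures show that 73 is wrong or that the trial is underpowered for its main effect; the documents give nothing against which to test that.

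**What to change.** Replace the ANOVA sentence with one within-person crossover model per lipid:

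- **Outcome.** The six-week fasting value at MIT 2 and MIT 4, from the draw taken before the test. This must be named, since "Blood samples (8 mL) will be collected before and after each MIT from the" antecubital vein.
- **Terms.** Fixed effects for treatment, period, sequence, exercise group and period-by-exercise; random participant effect.
- **Primary contrast.** Spirulina minus placebo at six weeks.
- **Departure to declare.** This analyses end-of-period values where Outcome measures says changes. The two agree in expectation only with complete washout. Report the six-week-change analysis, or one adjusted for the period baselines (MIT 1, MIT 3), as a sensitivity analysis.
- **Synergy.** In a second model add treatment-by-exercise, with sequence-by-exercise. Report the interaction with its confidence interval, and note that exercise is self-chosen and power is low.
- **If ordinary regression is used** for participants with both periods: take the primary effect from MIT 2 minus MIT 4 on sequence (+1/−1) and exercise group, without the product. Take the interaction from a second regression that adds the product with exercise coded 0/1. Do not read that second regression's sequence coefficient as the overall Spirulina effect.
- **Exclude** whole-study before/after change as a test of Spirulina.

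The rule for success across the four lipids must be stated separately.

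Cost: SAP wording, software that fits the model, and a little more analysis work; no new visits, samples or participants. The interaction test remains weak. The contrast also still relies on the "washout period of two weeks to remove the effects of treatment and avoid any" delayed effect. If a fraction r of the effect persisted to MIT 4, the end-of-period contrast would become τ(1 − r/2). If r persisted at MIT 3 only, end-of-period values would be unbiased and the six-week-change contrast would become τ(1 + r/2), for example 25% too large at r = 0.5.

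### Read literally, the planned before-and-after-the-study ANOVA has no place for six-week lipid data from participants who leave after period 1; the exercise contrast could be biased as a result

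*Combined protocol and SAP*

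**What the plan says.** The Statistical analysis section names one method for the treatment and group comparisons: to examine differences "between variables before and after the study and between the groups, an ANOVA" test is to be used. It gives no model terms, analysis set, missing-data rule or use for one-period data.

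Other sections fix when the outcome is measured:

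- Outcome measures: "The primary outcome measure will be changes in the plasma lipid profile after a" and then "six-week of treatment (plasma TAG, TC, HDL-c, and LDL-c by using standardized". This is one outcome per treatment period.
- Study design: two six-week treatments, described as 6 weeks, then 2 "weeks of washout period - 6 weeks for the second treatment".
- Maximum intensity tests: the day after the "first supplementation period, subjects will come back to perform the second MIT". Participants themselves choose the exercise group (GEx) or the non-exercise group (GNEx) before the first test.
- Sample collection and biochemical analysis: "Blood samples (8 mL) will be collected before and after each MIT from the" antecubital vein.
- Study design, sample size: "selecting a sample of 73 subjects with" stated alpha and power, then "fixed to 80 subjects in order to anticipate the possible desertions from the study".
- Participants' eligibility: participants are eliminated for attendance below 80% and/or a 20% body-weight change. Whether their data are kept is not stated.

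**The concern.** Someone who completes period 1 and then leaves has blood from MIT 1 and MIT 2, which is the whole of the primary outcome for one period. That person has no MIT 4. If the ANOVA really compares the start of the study with its end, a measured primary outcome goes unused.

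This matters mainly for exercise. The capsule comparison is within person, so a single period adds little to it. The exercise comparison is between persons, and Objectives makes the independent and synergistic effects of capsule and exercise the main aim. Only GEx has to train five days a week, so unequal desertion is plausible. If poor responders leave GEx more often, an analysis of finishers overstates the exercise effect. That would come on top of any confounding from participants choosing their own group.

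**Working it through.** **1. The plan's own figures.** The sample of 73 cannot be reproduced, because no effect size, SD, test family or sidedness is given. Taking the printed 0.85 as power, 73 corresponds to a two-sided paired effect of 0.355 SD of differences, or a two-group effect of 0.711 SD; neither can be confirmed. The desertion allowance is 80 − 73 = 7, or 7/80 = 8.75%.

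**2. Data held by a period-1 leaver.** MIT 1 and MIT 2 each have blood samples, so one complete six-week change exists. MIT 3 and MIT 4 are missing.

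**3. Assumed inputs (not in the documents).**

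- 40 GEx and 40 GNEx, with all 7 leaving after MIT 2.
- True exercise effect 0.50 SD.
- Correlation r = 0.3, 0.5 or 0.7 between a person's two period outcomes.
- Correlation c between poor period-1 response and leaving.

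**4. Bias with finishers only.** If the lowest fraction p of a group on a normal trait leaves, the mean of that trait among those who stay rises by λ(p) = φ(Φ⁻¹(p))/(1 − p). Period 1 is shifted by c·λ and period 2 by r·c·λ, so their average is shifted by c·λ·(1 + r)/2. The exercise bias is therefore

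c × [λ(GEx) − λ(GNEx)] × (1 + r)/2.

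For 6 GEx and 1 GNEx leavers, p = 0.15 and 0.025, so λ = 0.2743 and 0.0599. With c = 0.5, 0.5 × 0.2144 = 0.107. Multiplying by 0.65, 0.75 and 0.85 gives 0.070, 0.080 and 0.091 SD.

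| Leavers GEx/GNEx | c | Finishers-only estimate (true 0.50) | Bias |
|---|---|---|---|
| 6/1 | 0.5 | 0.570 to 0.591 | 14% to 18% |
| 5/2 | 0.5 | 0.541 to 0.554 | 8% to 11% |
| 4/3 | 0.5 | 0.514 to 0.518 | 3% to 4% |
| 6/1 | 0.2 | 0.528 to 0.536 | 6% to 7% |
| any | 0 | 0.500 | 0% |
| 7/0 (extreme) | 0.5 | 0.602 to 0.633 | 20% to 27% |

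Simulation of the 6/1, c = 0.5 case (600 trials per setting) agrees. Finishers only gives 0.565, 0.592 and 0.591; a model keeping period-1 data gives 0.498, 0.511 and 0.501.

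**5. Precision of the exercise contrast (6/1 split).** The finishers-only variance is [(1 + r)/2] × (1/34 + 1/39). In the all-periods analysis a finisher contributes information 2/(1 + r) and a one-period leaver contributes 1.

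| r | SE, finishers | SE, all periods | Reduction |
|---|---|---|---|
| 0.3 | 0.189 | 0.183 | 3.2% |
| 0.5 | 0.203 | 0.196 | 3.6% |
| 0.7 | 0.216 | 0.208 | 4.1% |

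**6. Spirulina contrast.** With 7 leavers, generalized least squares with a period effect cuts the variance by 3.3%, 2.3%, 1.4% and 0.5% at r = 0.3, 0.5, 0.7 and 0.9. In simulation with a true effect of 0.30, the estimate is about 0.30 under both analyses.

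**The case against.** The strongest reply is that the plan never says leavers are dropped. A comparison of MIT 1 with MIT 4 could not estimate the capsule effect, because by MIT 4 every finisher has taken both products. Before and after each period is the more coherent reading. It fits Outcome measures and the four-test schedule, and it would keep period-1 data. This stands: a reader might infer planned exclusion, but the documents support only a silence and a literal wording that leaves these records without a place.

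Other replies stand in part:

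- **Size.** A reader might take 14% to 18% as the expected bias. It belongs to one assumed split and one assumed link. Even there, 0.07 to 0.09 SD is less than half a standard error (0.19 to 0.22).
- **Information.** It is tempting to say one period carries nearly full information on exercise. Relative to two periods it carries (1 + r)/2, or 65%, 75% and 85% at r = 0.3, 0.5 and 0.7.
- **Elimination rule.** If attendance is counted over all 12 treatment weeks, a GEx participant leaving after week 6 has at most about 6/12 = 50% and meets the criterion. A new model would then recover nobody unless the analysis set also covers that rule. The text does not define the denominator.
- **Confounding.** Exercise is self-chosen, so its contrast is not protected by randomization even with no losses. Selective loss would add to that problem; it is not the only source of bias.
- **Missing at random.** When period-2 response drives leaving (6/1, c = 0.5), the all-periods model also overstates, at 0.52 to 0.54.

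**Conclusion.** The concern holds as a gap in the analysis plan and should be closed before analysis. Read literally, the stated ANOVA gives no place to a measured six-week primary outcome from a period-1 leaver, and nothing in the available text supplies one.

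Under a finishers-only analysis with 7 desertions, the exercise effect could be overstated by roughly 0% to 18% of an assumed 0.50 SD, for splits from 4/3 to 6/1 and c from 0 to 0.5. Only the extreme of all 7 losses in GEx with c = 0.5 goes beyond that range. If leaving is unrelated to response, desertion adds no bias. The Spirulina estimate is essentially unaffected. The precision gain for exercise, about 3% to 4%, is minor; the reason to act is possible avoidable bias in a contrast that is already non-randomized. The documents give neither the split, the response link nor the within-person correlation, so no single figure should be quoted as the expected bias.

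**What to change.** Replace the ANOVA in Statistical analysis with a likelihood-based linear mixed model:

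- One record per participant-period that has an end-of-period value, with a random participant effect.
- Fixed effects for sequence, period, capsule, exercise group and capsule-by-exercise.
- Starting lipid values handled so that period-2 starting values do not distort the capsule effect, for example by using the pre-period-1 value as the covariate.

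State that observed period data stay in the analysis both for participants who leave and for those who meet the elimination criteria. This is a rule about the analysis set only. Tabulate losses by exercise group and period, show the complete-case result as a sensitivity analysis, and describe the exercise contrast as non-randomized.

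The cost is new wording and a routine model fit, with no added visits or samples. The team should confirm that the named software, GraphPad Prism 6, can fit this model, or name another package. The remaining limits are that the model relies on missing at random and that it does not recover people who leave before the second MIT.
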